Thus, specifically with regard to percutaneous nephrostomy, in some situations antibiotic prophylaxis may not be carried out, as suggested by a 1991 study, in patients at low risk of sepsis related to the procedure (14% of sepsis in those patients who were not given antibiotic prophylaxis and 10% of sepsis in those who received antibiotic prophylaxis, $p = 0.75$). However, for patients considered to be at high risk of urinary focus sepsis after the procedure (the elderly, those with diabetes *mellitus*, those with bladder dysfunction, patients using a delayed bladder catheter, patients who had undergone previous manipulation of the urinary tract, patients with uretero-intestinal anastomosis, stones and bacteriuria) the same study found that in patients who did not receive antibiotic prophylaxis the sepsis rate was 50% and in those who received antibiotic prophylaxis the sepsis rate was 9%, $p = 0.03$ ²². This study evaluated malignant and benign ureteral obstructions, mainly caused by calculi, and 12/56 (21.4%) of the patients developed signs of sepsis after percutaneous nephrostomy, but 9 of them had ureteral calculi and in 7 of these 12 patients percutaneous nephrostomy was used as an access for percutaneous nephrolithotomy ⁽²²⁾.

It is important to note that the proportion of sepsis in this study is high due to a possible latent ureteral infection secondary to the presence of calculi, which may be an important selection bias, and thus it is not possible to compare these high sepsis rates with other clinical situations requiring percutaneous nephrostomy catheters ^{22, 35}. The population of patients undergoing percutaneous nephrolithotomy with latent infections secondary to calculous disease is different from populations without calculi because the infection, even if latent, in the former is prior to the procedure, and it is not possible to attribute any sign of infection to the decompression performed by percutaneous nephrostomy and then judge it as a life-threatening procedure ⁽³⁵⁾.

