A retrospective cohort carried out at this institution evaluated 180 percutaneous nephrostomies (87 first passes and 93 catheter changes) over a 3-year period. The occurrence of urinary tract infection related to the nephrostomy catheter was verified up to 7 days after the procedures, with 1.2% of urinary tract infection related to the nephrostomy catheter being identified after its first passage and 11.4% after catheter changes ($p = 0.01$)⁴³. In the first passages, there was no statistically significant difference in urinary infection rates when the patient received antibiotic prophylaxis or

not (0% *versus* 1.5%, respectively; $p = 0.999$). In catheter changes, even without statistical significance ($p = 0.146$), the urinary infection rate was 21.4% in those patients who did not receive antibiotic prophylaxis; 14.8% in those who received empirical antibiotic prophylaxis and 6.4% in those who received targeted antibiotic prophylaxis (with antibiotics guided by a previously collected uroculture result)⁴³. Despite the potential bias in results due to its retrospective nature, this study demonstrates a reality in clinical practice and also a possible solution both to prevent urinary infections in this population and to help rationalize the use of antibiotics.

Finally, a prospective study assessed the incidence of urinary tract infection after nephrostomy catheter changes without antibiotic prophylaxis and found that out of 126 catheter change procedures, 13.5% had infectious complications. Just over half (52.9%) required antibiotic treatment and only 1 patient was hospitalized for such treatment, but without threatening the patient's life, according to the authors⁽⁴⁴⁾.

Consequently, there are more doubts than certainties about antibiotic prophylaxis in percutaneous nephrostomy in cancer patients.

Based on what has been said so far, two fundamental questions can be posed. Firstly: would it be necessary to carry out antibiotic prophylaxis for the first passage of the percutaneous nephrostomy catheter to prevent urinary infection related to the procedure? And secondly: can uroculture-guided antibiotic prophylaxis be superior in preventing urinary tract infection when compared to empirical antibiotic prophylaxis after percutaneous nephrostomy catheter changes guided by imaging? These are the questions that guide this research project.

2.

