4.10.1. Definitions

In order to carry out this study, it is necessary to establish some concepts, some of which are not yet standardized in the medical literature:

- **Urinary tract colonization:** occurs when there is a positive uroculture result (presence of infectious agents such as bacteria or fungi) in the absence of clinical signs suggestive of infection. In these cases, antibiotic treatment is not necessary (45).
- **Urinary tract infection:** occurs when there are signs and symptoms suggestive of local infection, such as cystitis (bladder infection or lower urinary tract infection) or pyelonephritis (kidney infection or upper urinary tract infection) associated with a positive uroculture result, requiring treatment with antibiotics ^{3, 19, (46)}.

- **Urinary tract infection related to the percutaneous nephrostomy procedure:** when the urinary tract infection occurs shortly after the procedure has been carried out, in this case, percutaneous nephrostomy (first pass or catheter changes).
- **Urinary tract infection related to the nephrostomy catheter:** when the urinary tract infection occurs at another time unrelated to the procedure and in the presence of the nephrostomy catheter and in the absence of another focus justifying the infection.

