4.10.3. Procedure for changing the catheter

Catheter changes take place electively approximately every 90 days after the previous procedure (first pass or previous catheter change), scheduled during outpatient follow-up. However, this change can happen earlier than planned due to situations such as catheter obstruction and migration, or even catheter-related urinary tract infection.

This group will be made up of patients undergoing percutaneous nephrostomy catheter exchange and will study the use of empirical or targeted antibiotic prophylaxis documented in medical records to be reviewed at the two hospitals.

The Jales Cancer Hospital will study targeted antibiotic prophylaxis, which consists of collecting the following laboratory tests around 7 days before the procedure

to change the nephrostomy catheter(s) to guide the antibiotic to be used for prophylaxis: serum creatinine and urea levels, urine samples for tests such as urine summary (or type I urine) and uroculture with antibiogram. If the tests are not carried out prior to the procedure or if the uroculture does not show a specific bacterial agent, the procedure will be studied according to empirical antibiotic prophylaxis.

The Hospital de Câncer de Barretos will study the empirical antibiotic prophylaxis carried out according to daily clinical practice, recorded in the medical records to be reviewed of patients undergoing percutaneous nephrostomy catheter exchange.

The proportion of urinary tract infections that developed within 7 days of the procedure will be studied. A procedure-related urinary tract infection is considered to be any report in the medical record of clinical signs and symptoms associated with uroculture results (see definition in item 4.10.4.) and the location of the respective treatment will be documented: outpatient, inpatient or intensive care unit (ICU).

It will be documented whether there is evidence reported in medical records of urinary tract infections or the presence of bladder fistulas prior to the procedure.

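### At Jales, the culture result and whether a culture was done decide the arm for catheter changes, so guided and empirical prophylaxis are compared in differently selected groups, with a bias of unknown net direction

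*Protocol*

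**What the plan says.** The second of the study's two guiding questions (Protocol 1.5.2.3) is: "can uroculture-guided antibiotic prophylaxis be superior in preventing urinary tract infection when compared to empirical antibiotic prophylaxis" after catheter changes. Section 4.10 repeats this contrast for the analysis of changes.

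Section 4.10.3 sets the arms:

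- **Jales:** "The Jales Cancer Hospital will study targeted antibiotic prophylaxis, which consists of collecting the following laboratory tests around 7 days before the procedure", so that the result can direct the choice of antibiotic.
- **Barretos:** "The Hospital de Câncer de Barretos will study the empirical antibiotic prophylaxis carried out according to daily clinical practice". No culture-based selection is described.
- **Exceptions at Jales:** one sentence names two. The first is "If the tests are not carried out prior to the procedure". The second is "if the uroculture does not show a specific bacterial agent, the procedure will be studied according to empirical antibiotic prophylaxis".

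Protocol 4.12 and the SAP plan chi-square or Fisher tests, then a logistic regression on variables with p below 0.20 in the univariate step. Neither document plans an analysis by strategy, an adjustment fixed in advance for pre-change culture status or hospital, or a sensitivity analysis for the arm definition. The SAP gives no arm definition of its own, so section 4.10.3 governs.

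**The concern.** Section 4.10.3 first describes a strategy (culture, then choose) and then allocates tested Jales changes by what the culture showed. Among them, the result alone fixes the arm.

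Culture status is plausibly prognostic on the protocol's own account:

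- Section 1.5.1 calls biofilm on the catheter a reservoir that can perpetuate infection or facilitate a new episode.
- The high-risk list in section 1.5.2 includes "patients with uretero-intestinal anastomosis, stones and bacteriuria".
- Section 4.7 excludes changes done while an infection is being treated. The guided arm is thus largely the colonised group of section 4.10.1, defined by a "positive uroculture result (presence of infectious agents such as bacteria or fungi) in the absence of clinical signs suggestive of infection".
- The outcome in section 4.10.4 itself needs a culture above 100,000 CFU/ml. A patient already growing an organism is therefore nearer to meeting it.

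At stake is one of the study's two questions and part of its primary objective. A difference between arms could reflect who was placed in each arm and not what the prophylaxis did. The first-passage comparison is not affected.

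**Working it through.** **1. Figures in the plan.** The procedure count reproduces: 372 + 358 = 730. The SAP mentions a power calculation but gives no value or inputs, so there is none to check. The only between-arm data are from the earlier institutional cohort (1.5.2.3): infection after changes in 21.4% with no prophylaxis, 14.8% empirical, 6.4% targeted, 11.4% overall, p = 0.146. The integer counts that fit are 3/14, 4/27 and 3/47, total 10/88 = 11.4%. The exact test on these gives p = 0.146. The protocol does not say how that cohort assigned culture-negative or untested changes, so it neither confirms nor refutes a bias.

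**2. Inputs.** From the documents: overall risk R = 11.4%. Not in the documents, so assumed:

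| Symbol | Meaning | Range |
|---|---|---|
| s | Jales share of changes | 30–70% |
| q | share of tested Jales changes with an isolate | 50–85% |
| k | risk with isolate ÷ risk without | 1.5–3 |
| u | untested share of Jales changes | 10–30% |
| r | untested risk ÷ mean tested risk | 1–3 |

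The model has no true effect of strategy and the same overall risk at both hospitals. A fair comparison would therefore give a risk ratio of 1.00.

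**3. No-isolate route only (u = 0).**

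- Risk without isolate: p0 = R ÷ (qk + 1 − q).
- Guided arm: k × p0.
- Empirical arm: [(1 − s)R + s(1 − q)p0] ÷ [(1 − s) + s(1 − q)].

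With s = 0.5, q = 0.5, k = 2: p0 = 0.114 ÷ 1.5 = 0.076. Guided is 15.2%. Empirical is (0.057 + 0.019) ÷ 0.75 = 10.1%. The risk ratio is 1.50. Over the assumed ranges it runs from 1.07 to 2.05, always against guided. With k = 1 it is 1.00, because this route adds no bias if colonisation does not raise risk.

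**4. Adding the untested route (s = 0.5).**

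- Mean tested risk: m = R ÷ (1 − u + ur).
- p0 = m ÷ (qk + 1 − q), and guided is again k × p0.
- The empirical arm gains a share s × u at risk r × m; its no-isolate share becomes s(1 − u)(1 − q).

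With q = 0.7, k = 2, u = 0.2, r = 2: m = 0.114 ÷ 1.2 = 0.095 and p0 = 0.095 ÷ 1.7 = 0.0559. Guided is 11.2%. Empirical is (0.057 + 0.019 + 0.0067) ÷ 0.72 = 11.5%. The risk ratio is 0.97.

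| Untested risk | Apparent risk ratio, guided/empirical |
|---|---|
| average (r = 1) | 1.08 to 1.75 |
| 2 to 3 times | 0.57 to 1.52 |

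**5. Effect on a real difference.** Assume 179 changes per hospital, none untested, and risks of 14% at Barretos, 9% at Jales with an isolate and 2–4% without. Let f be the share without an isolate. The difference by strategy is 14% − [(1 − f) × 9% + f × (2–4%)]. The difference as written is [14% + f × (2–4%)] ÷ (1 + f) − 9%. At f = 30% these are 6.5–7.1 points by strategy and 2.2–2.7 as written. At f = 20–50% they are 6.0–8.5 and 1.0–3.3.

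**6. Can regression repair it?** Within tested Jales changes no culture result occurs in both arms, so there is nothing to adjust within. For Barretos no pre-change culture is described, so the covariate may be missing for most of the comparator. A p < 0.20 screen addresses neither problem.

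**The case against.** **The grouping can be defended as prophylaxis received.** Section 1.5.2.3 describes targeted prophylaxis as antibiotics chosen from an earlier culture result. Without an isolate no antibiogram can direct the drug, so calling that change empirical is coherent. This stands as a question one may ask. But a guided arm made up of changes with an isolate then needs a comparator with an isolate, and the plan has none.

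**The bias may be small.** Section 1.5.1 says colonisation begins as soon as the catheter is placed, and changes come at about 90 days, so few cultures may lack an isolate. With 95% positive, s = 0.5 and k = 2, the step 3 ratio falls to 11.7% ÷ 11.1% = 1.05. With 5% negative, step 5 gives 4.4–4.5 points as written against 5.3–5.4 by strategy. This stands: the size depends on a share that the documents do not report.

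**The evidence that bacteriuria raises risk is thin.** The high-risk list comes from a 1991 study of sepsis, and the protocol itself says its rates do not transfer, because stones drove them. Nor are the moved changes all culture-negative: having no specific bacterial agent could cover mixed or fungal growth, and section 4.10.1 counts fungi as colonisation. Both points stand.

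**A reader might infer that the comparison is biased against guided prophylaxis, and that a true benefit could be reversed.** The documents do not support this. The same sentence moves untested changes, and section 4.10.3 says "this change can happen earlier than planned due to situations such as catheter obstruction and migration, or even catheter-related urinary tract infection". If those are the untested ones, higher-risk changes may load the empirical arm and favour guided. The exclusion of changes under treatment for infection removes some of them, but an unknown number. As for reversal, every case in step 5 shows a smaller benefit and none a change of sign.

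**Conclusion.** The concern holds as a selection problem of undetermined net direction. That the Jales arms depend on culture result and test availability follows from the text and needs no assumption. The no-isolate route acts against guided prophylaxis if colonisation raises risk; the untested route may act in its favour. With no true effect, the apparent risk ratio can fall well below or well above 1 under the assumed inputs. The documents give neither the Jales share, nor the shares without an isolate or untested, nor risk by culture status, so the size cannot be narrowed. A difference, or a lack of one, under the current grouping cannot be attributed to guided prophylaxis. This should be corrected before the catheter-change result is interpreted.

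**What to change.** 1. **Primary comparison of changes by strategy:** keep all Jales changes in the guided arm, whatever the culture showed and including those not tested, against Barretos changes. In the model above this gives 11.4% in both arms, risk ratio 1.00, provided that case mix is equal at the two hospitals. The documents do not establish that.
2. **Sensitivity analysis:** count as guided only changes with a pre-change culture obtained, whatever its result. Selection by test availability remains here, so it should not be primary.
3. **Separate reporting:** give counts and infection rates for changes with a positive culture, with no specific isolate, and untested. State how mixed and fungal growth are coded.
4. **Like-for-like contrast:** compare culture-positive changes across hospitals where Barretos pre-change cultures exist.
5. **Secondary:** keep the grouping of section 4.10.3, labelled as such.

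The cost is mainly re-coding. Protocol 4.10.5 lists uroculture and antibiogram, and 4.12 links procedures to patients. Culture date is not named among the variables, so some return to the records may be needed. The guided arm will be diluted by changes where the culture did not alter the drug. The arm contrast will nearly coincide with hospital, so residual site confounding remains and must be stated as a limitation.

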4.10.4. Urinary tract infection

A urinary tract infection will be considered to be the presence of clinical signs and symptoms suggestive of infection, such as fever (axillary temperature greater than 37.8°C), chills, low back pain, pain at the wrist-percussion of the lumbar region and/or the presence of cloudy urine in the collection bag, plus a uroculture with the presence of microorganisms (no more than two) with more than 100,000 CFU/ml.

If the urinary tract infection is diagnosed 7 (seven) days after the procedure (first catheter passage or change), it will be considered a procedure-related urinary tract infection.

If a urinary tract infection is diagnosed between catheter changes, it will be considered a catheter-related urinary tract infection.

The laboratory tests to be studied will be blood count, creatinine and urea, C-reactive protein, type I urine, uroculture and antibiogram and samples of blood cultures and antibiograms collected at the time of diagnosis of the urinary tract infection.

If the participant receives treatment for a possible urinary tract infection occurred between catheter changes at another service, it will be considered an infection if there is an improvement in the symptoms reported by the participant in the medical records and the antimicrobial used for the treatment will be verified.

The antibiotic(s) used for treatment will be duly studied and registered

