1.4.3. Infectious complications

Even though the aforementioned review showed rates of pyelonephritis and septic shock related to percutaneous nephrostomy of up to 10%, the proportions of infectious complications can vary in the literature:

- a) without evidence of urinary infections ^{23, (24)} ;
- b) 8.5% of catheter insertion site infections ⁽²⁵⁾ ;
- c) 10.3% of intra-renal or peri-renal abscesses ⁽²⁵⁾ ;
- d) 3.7% to 15% of febrile episodes ^{11, 14, (26)} ;
- e) 11.6% to 38.1% urinary tract infection ^{7, 9(,) (10)(,) (19)} ;
- f) 7% of infections related to percutaneous nephrostomy ⁽²⁷⁾ ;
- g) 3.8% to 19% pyelonephritis ^{3, 14} and
- h) 9% to 50% septicemia ^{9, (22)} .

In studies of patients undergoing percutaneous nephrostomy for malignant ureteral obstruction alone, catheter-related urinary infection ranged from 3.8% to 38.1% ^{3, 7(,) (9)(,) (10)(,) (14)(,) (19)(,) (25)} .

These disparate values exist because there is no robust clinical evidence on the best way to diagnose nephrostomy catheter-related urinary tract infection, especially in cancer patients, i.e. the definitions used in the studies are methodologically varied ⁽¹⁹⁾ .

Of the proportions of urinary infection cited above, seven studies do not methodologically define nephrostomy catheter-related urinary tract infection ^{7, 9(,) (10)(,) (23-25)} . One study defines urinary infection as fever and flank pain accompanied by bacteriuria or pyuria with no other focus, but does not mention uroculture and time after procedure ¹⁴ . Another study defines an infectious complication only as fever (temperature greater than 38°C) within 30 days of follow-up ²⁶ . A third study defines temperature as less than 36°C or greater than 38°C, associated with a white blood cell count greater than 10,000 cells/mL, positive uroculture and blood culture ⁽²⁷⁾ .

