Bahu *et al.* defined pyelonephritis as at least 1 sign or symptom (fever greater than 38°C, pain on costovertebral percussion and/or flank pain) associated with uroculture with growth of no more than two species of microorganisms greater than or equal to 10⁵ CFU/ml at 90-day follow-up after the procedure ³ . Szvalb *et al.* define infection related to percutaneous nephrostomy as any clinical symptom (fever, chills, pain on costovertebral percussion, hypotension and/or cellulitis at the catheter entry site) not explained by another diagnosis associated with uroculture with bacterial growth greater than or equal to 10⁴ CFU/ml at a follow-up of 100 days after the procedure ¹⁹ . The last study mentioned only signs of sepsis: chills and fever at the time of the procedure with or without hypotension ⁽²²⁾ .

Inaccurate diagnosis can lead to inadequate treatment, resulting in irrational use of antimicrobials and, consequently, future infections with multi-resistant bacteria. This is a cause for concern, as it aggravates the clinical condition of patients with neoplasms who are already immunocompromised, both because of the tumor and the cancer treatment itself.

1.5. Is it possible to avoid a urinary tract infection related to a percutaneous nephrostomy catheter?

At the same time as there is no consensus on the definition of nephrostomy-related urinary tract infection, there is also no consensus on its prophylaxis. In order to assess it, it is necessary to take into account the formation of a biofilm of microorganisms on the catheter (perhaps this is the most important factor) and the use of antibiotics.

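### The rule that counts procedure-related UTI, the primary outcome, has no condition that another focus be absent, so fever with another documented explanation can be counted as an event

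*Protocol*

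**What the plan says.** Protocol 3.1 makes the rate of procedure-related UTI the primary objective. Two sections define the event.

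- **Protocol 4.10.1 (concepts).** UTI in general needs "signs and symptoms suggestive of local infection", meaning cystitis or pyelonephritis, with a positive culture and "requiring treatment with antibiotics". Procedure-related UTI adds only timing: "when the urinary tract infection occurs shortly after the procedure has been carried out". Catheter-related UTI, a secondary outcome, adds "in the absence of another focus justifying the infection".
- **Protocol 4.10.4 (operative rule).** Sections 4.10.2 and 4.10.3 send the reader here for events within 7 days. The clinical part is the "presence of clinical signs and symptoms suggestive of infection, such as fever (axillary temperature greater than 37.8°C), chills, low back pain" and other items in an and/or list. The culture part is at most two organisms above 100,000 CFU/ml. Nothing is said about another focus for either UTI type, and the phrases on local infection and antibiotic treatment do not reappear. Sampling at the time of diagnosis is mentioned, but it is unclear whether that covers the urine culture or only the blood cultures.

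Protocol 1.4.3 describes earlier studies that did set such a condition. One required "fever and flank pain accompanied by bacteriuria or pyuria with no other focus"; another required symptoms "not explained by another diagnosis".

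For catheter changes, 4.10.3 makes a positive culture about 7 days beforehand the entry condition for the targeted group: "if the uroculture does not show a specific bacterial agent, the procedure will be studied according to empirical antibiotic prophylaxis". Untested changes also go to the empirical group.

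**The concern.** Cancer patients with a nephrostomy can have fever for reasons outside the urinary tract, such as pneumonia, neutropenia or the tumour. Many also carry organisms in the urine; Protocol 1.5.1 says the catheter is colonised from insertion. An abstractor who applies 4.10.4 literally would count a fever of that kind, together with a qualifying culture, as procedure-related UTI. The exclusions in 4.7 remove patients on treatment for UTI or on suppressive antibiotics, but not patients with an infection elsewhere.

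At stake are the UTI rate itself, at first passages and at changes, and the comparison of targeted with empirical prophylaxis at changes. False events that the type of prophylaxis does not influence would usually make the two groups look more alike. If a pre-change culture may also serve as the event culture, the targeted group is especially exposed, because every procedure in it has a positive one.

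**Working it through.** **1. The passages side by side**

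| Condition | 4.10.1, general UTI | 4.10.1, procedure-related | 4.10.1, catheter-related | 4.10.4, both types |
|---|---|---|---|---|
| Signs of local infection | yes | inherited | inherited | not stated |
| Needs antibiotic treatment | yes | inherited | inherited | not stated |
| No other focus | no | no | yes | not stated |
| CFU threshold | no | no | no | yes |
| Culture dated to the event | no | no | no | unclear |

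The gap for the primary outcome is therefore present in both sections.

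**2. Base figures**

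No figure in the plan bears directly on this point. The nearest are the earlier institutional cohort's rates at catheter change (Protocol 1.5.2.3): 14.8% empirical and 6.4% targeted. Risk ratio = 0.064/0.148 = 0.43; difference = 8.4 points. Counts of 3/14 (no prophylaxis), 4/27 (empirical) and 3/47 (targeted) reproduce that cohort's percentages, its overall 11.4% (10/88) and its p-value of 0.146 by the Fisher-Freeman-Halton exact test. The base rates thus appear to rest on 4 and 3 events.

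**3. Model**

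Observed rate = p + (1 − p) × f × c, where
- p is the true UTI risk (the rates above);
- f is the share with fever from another cause within 7 days (assumed);
- c is the share with a qualifying culture, cT in targeted and cE in empirical (assumed).

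Example with f = 2%, cT = 1, cE = 0.5:
- targeted = 0.064 + 0.936 × 0.02 × 1 = 0.083
- empirical = 0.148 + 0.852 × 0.02 × 0.5 = 0.157
- risk ratio = 0.0827/0.1565 = 0.53

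Power below is for a two-sided 5% test with the 358 changes split 1:1 and taken as independent. The actual split is not given.

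| f | cT | cE | Empirical | Targeted | Risk ratio | Power |
|---|---|---|---|---|---|---|
| 0 | – | – | 14.8% | 6.4% | 0.43 | 73.5% |
| 2% | 1 | 0.5 | 15.7% | 8.3% | 0.53 | 58% |
| 2% | 1 | 1 | 16.5% | 8.3% | 0.50 | 66% |
| 2% | 0.5 | 0.8 | 16.2% | 7.3% | 0.45 | 74% |
| 5% | 1 | 0.5 | 16.9% | 11.1% | 0.65 | 36% |
| 5% | 1 | 1 | 19.1% | 11.1% | 0.58 | 56% |
| 5% | 0.5 | 0.8 | 18.2% | 8.7% | 0.48 | 75% |
| 10% | 1 | 0.5 | 19.1% | 15.8% | 0.83 | 13% |

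**4. Which way it goes**

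- Targeted gains more false events, in percentage points, only if 0.936 × cT > 0.852 × cE, that is cT > 0.91 × cE.
- The risk ratio moves toward 1 if (0.936 × cT)/(0.852 × cE) > 0.432, that is cT > 0.39 × cE.

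Between these two thresholds the ratio is diluted although the empirical group gains more false events. In the row with f = 5%, cT = 0.5 and cE = 0.8, empirical gains 3.4 points and targeted 2.3; the ratio moves to 0.48, the absolute difference widens to 9.5 points, and power does not fall.

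**5. How large f could be**

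The documents give no rate of non-urinary fever. Protocol 1.5.2.3 cites 4.5% with fever over 30 days in a mixed set of urological procedures, and 1.4.3 cites 3.7% to 15% with febrile episodes. Both are totals that would include urinary fever. A value of 2% within 7 days fits under the 4.5% figure; 5% and 10% exceed it and are shown only to complete the range.

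**The case against.** **The general definition already restricts the event.** Procedure-related UTI is a subset of UTI in 4.10.1, which asks for local infection needing antibiotics; pneumonia is not that. The SAP also checks whether urinary white cells, leukocytosis and culture informed the treatment decision, which captures part of the clinician's judgement. So the reading that fever from any cause always counts goes too far. What remains is that 4.10.4, the section to which the abstractor is sent, says something looser, and that a need for antibiotics does not separate UTI from pneumonia or febrile neutropenia.

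**The contrast between the two UTI types is only in 4.10.1.** This is correct: 4.10.4 treats both alike. The condition should therefore be added for both.

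**A bias against targeted prophylaxis.** A reader might infer that false events fall mostly in the targeted group because all its patients are colonised by rule. The documents do not support this. The rule in 4.10.3 concerns a culture about 7 days before the change, with no CFU threshold. Positivity at the event, after a culture-directed antibiotic and a new catheter, is not reported. Colonised patients are in the empirical group as well, since untested changes go there.

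**The sizes are soft.** This stands. The values of f and c are assumed. If the earlier cohort also counted fever with another focus, its rates already contain such events and the model counts them twice.

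**Scope.** The first-passage comparison (372 of 730 procedures) has no targeted group, so the risk-ratio arithmetic does not apply there; inflation of the rate does. Appendix II is not available, so a field for another focus may already exist.

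**Conclusion.** The defect is real and limited. The primary outcome has no condition on another focus in either section, and the operative rule is looser than the concept definition. Read literally, 4.10.4 admits fever that has another documented explanation.

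The consequences are a somewhat inflated UTI rate and, whenever targeted positivity exceeds about 0.39 times empirical positivity, a risk ratio pulled toward 1. The illustration that best fits the cited fever figures takes 0.43 to about 0.53, and rests on an assumed 2% fever rate, assumed 100% versus 50% culture positivity, and base rates from a small cohort. No net direction between the groups in absolute terms can be stated. The exposure is greatest if the pre-change culture is allowed to serve as the event culture, which 4.10.4 does not clearly rule out.

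**What to change.** Reconcile 4.10.1 and 4.10.4 so that one definition governs:

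1. Add to 4.10.4, for both UTI types: *and no other focus recorded in the chart that explains the signs*. State whether the conditions on local infection and antibiotic treatment in 4.10.1 also apply.
2. Require that the qualifying urine culture be collected at the time of the event, so that a pre-change culture cannot serve. The existing provision for episodes treated at another service needs its own wording, because a culture may not be available.
3. Record any alternative focus, and classify those episodes without reference to the prophylaxis group.
4. List the reclassified episodes by group, and run one sensitivity analysis that counts them as UTI.

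The cost is small. The SAP is written largely in the past tense, so extraction may be finished, but only counted events need a recheck. If the earlier cohort's rates apply, that is about 0.114 × 358 + 0.012 × 372 = 40.8 + 4.5, or roughly 45 charts. The UTI rate will be slightly lower. The change also makes the outcome depend on how well each hospital documents other foci, and hospital is partly aligned with prophylaxis group at changes. The list by group and the sensitivity analysis let a reader judge that.
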